6.3.4 Full analysis set last observation carried forward (LOCF)

For the analysis of all Week 52 efficacy endpoints, the full analysis set is a subset of randomized analysis set including patients who take at least one randomized investigational product dose, have non-missing baseline and a post baseline efficacy data. The missing Week 52 efficacy endpoints will be replaced by last observed value after baseline. Missing baseline (Visit 3) data will be estimated by a single value assessed at Visit 1, if one exists. Analysis of efficacy variables at Week 52 will be supplemented by the results from the full analysis set.

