Eligible patients will be given placebo in a single-blind fashion (blind to the patient only) at Visit 2 and start open-label metformin during the 2-week lead-in period. Patients on metformin will be treated with 1500, 2000, 2500 or 3000 mg of open-label metformin for the

duration of the study (see Section 3.4.2 for metformin doses to be used). The aim is that the open-label metformin dose should remain stable throughout the study.

The patients will be counselled on dietary and life-style modifications according to usual clinical routine. A glucometer and a patient diary will be handed out and the patients will be instructed to monitor their blood glucose at least every second day. Information about hypoglycaemic events should be entered into the patient diary.

Visit 2 should preferably be done at the clinic, but may be performed as a telephone visit if it is clear before the scheduled visit that the patient is not eligible due to the laboratory results from Visit 1.

Randomized treatment period (Period C):

The patients will be randomized at Visit 3 (baseline) and the double-blind treatment period will start. Either saxagliptin 5 mg plus open-label metformin or glipizide 5 mg plus open-label metformin will be given using a double-dummy technique. During the randomized treatment period dietary and life-style modification will be reinforced.

Titration period (Visits 4-9)

Patients in the glipizide plus metformin arm will be titrated to optimal effect (FPG \leq 6.1 mmol/L, \leq 110 mg/dL) or the highest tolerable dose during 18 weeks. Glipizide (4 doses) will be initiated at 5 mg per day (morning dose), and titrated in 3-week intervals to a maximum of 20 mg per day. The titration steps will be 10 mg per day (morning dose) followed by 15 mg per day (10 mg as morning dose and 5 mg as evening dose) and 20 mg (10 mg as morning dose and 10 mg as evening dose). In patients for whom titration was not medically indicated at Week 3, re-assessment for titration will occur at Week 6, 9, 12, 15, and 18. The decision for titration will be based on FPG measured at the study centre, using a glucose analyser provided by AstraZeneca. The investigational product (IP) glipizide can be down-titrated once during the titration period if hypoglycaemic events occur. Treatment may thereafter be up-titrated once during the titration period.

Patients on saxagliptin will remain on 5 mg throughout the study, no titration will be possible.

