3.2.1.3 Choice of outcome variables

In the regulatory guidelines for type 2 diabetes (CPMP 2002), HbA1c is the prescribed measure for determination of glycaemic control and is therefore chosen as the primary variable. As a member of DPP-4 inhibitors, saxagliptin leads to enhanced glucose dependent insulin secretion: low risk of hypoglycaemia and even weight loss may be expected. The

Clinical Study Protocol Drug Substance Saxagliptin Study Code D1680C00001 Date

incidence of hypoglycaemia over time and weight changes from baseline are therefore chosen as important secondary safety endpoints in part to characterise the saxaglipin therapy.

It is strongly believed that saxagliptin treatment may protect and/or promote pancreatic β-cell function; hence the saxagliptin therapy may be more durable and the patients may be more efficient in insulin secretion over time than the glipizide add-on therapy to metformin. The mean slopes of linear regressions of change from Week 24 in HbA1c after Week 24 will address the durability, or the rate of rise of HbA1c, over the 52 weeks of randomized treatment period. It is assumed that the nadir of HbA1c reduction may be observed as early as 24 weeks post first dose.

Other measures attempted in this protocol to better understand the mechanistic effects of saxagliptin are these other secondary efficacy outcome variables: The \(\beta\)-cell function will also be measured by HOMA-2 and insulinogenic index; insulin sensitivity will be measured by OGIS and Matsuda Index; OGTT responses; and the lipids variables (TC, LDL-C, HDL-C and TG).

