6.3.3 Per protocol analysis set

For the analysis of Week 52 primary efficacy endpoint and all secondary efficacy endpoints, the PP analysis set is a subset of full analysis set including patients who have completed the 52 weeks of randomized treatment period and have no reasons for exclusions.

These exclusions from the PP analysis set will include but not be limited to the patients who took prohibited concomitant medications, non-compliance to investigational product and major deviations of study procedures. The exclusions from the PP analysis set will be explicitly defined in SAP prior to Week 52 database locking. The non-inferiority conclusion pertaining to the primary endpoint will be drawn primarily based on results from per protocol analysis set and complementally based on full analysis set (see Section 6.3.4).

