6.4 Method of statistical analysis

6.4.1 Analysis of double-blind treatment Period C

The primary efficacy analysis to establish non-inferiority with 0.35% non-inferiority limit on the change in HbA1c from baseline to Week 52 will be performed on a per protocol analysis set using ANCOVA. The model will use treatment group as a fixed effect and baseline value as a covariate. Within the framework of the ANCOVA model, point estimates and the two-sided 95% confidence intervals for the mean change within each treatment group as well as for the differences in mean change between the saxagliptin plus metformin treatment arm and the glipizide plus metformin treatment arm will be performed. Saxagliptin plus metformin will be considered not inferior to glipizide plus metformin if the upper limit of the two-sided 95% confidence interval of the difference in change in HbA1c from baseline to Week 52 between saxagliptin plus metformin and glipizide plus metformin is less than 0.35%.

Analyses of the secondary efficacy endpoints will be performed using ANCOVA methods for change from baseline in glucose related endpoints, β -cell functions, and insulin sensitivity. The ANCOVA model will use treatment group as a fixed effect and baseline value as a covariate. Within the framework of the ANCOVA model, point estimates and the two-sided 95% confidence intervals for the mean change within each treatment group as well as for the differences in mean change between the two treatment groups will be reported.

Repeated measures analysis may be performed on selected efficacy variables over time as sensitivity analysis.

Hypoglycaemic events and body weight changes are considered as safety variables and are specified as important secondary variables supporting the treatment of saxagliptin. Proportion of patients reporting at least one episode of hypoglycaemic event over the 52-week treatment period will be compared between the two treatment groups using a two-sided Fisher's exact test. ANCOVA method comparing the two treatment groups will be used for change from baseline in body weight at Week 52, where the model will include treatment as a fixed effect and baseline as a covariate.

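### The only non-inferiority analysis that keeps early leavers carries their last HbA1c forward; the bias can go either way and matters mainly when the true difference is near the 0.35% limit

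*Protocol*

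**What the plan says.** **Missing data.** Section 6.3.4 fixes last observation carried forward (LOCF) for the full analysis set: "The missing Week 52 efficacy endpoints will be replaced by last observed value after baseline".

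**Role of the set.** Under Section 6.3.3 the non-inferiority conclusion is "drawn primarily based on results from per protocol analysis set and complementally based on full analysis set". The same section limits the per protocol set to "patients who have completed the 52 weeks of randomized treatment period and have no reasons for exclusions".

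**Decision rule.** Section 6.4.1 requires the "upper limit of the two-sided 95% confidence interval of the difference in change in HbA1c from baseline to Week 52" to lie below 0.35%.

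**Alternative.** Section 6.4.1 leaves it open and does not tie it to HbA1c: "Repeated measures analysis may be performed on selected efficacy variables over time as sensitivity analysis".

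**Expected course of HbA1c.** In Section 3.1 glipizide starts at 5 mg and is "titrated in 3-week intervals to a maximum of 20 mg per day", within an 18-week titration period; saxagliptin stays at 5 mg. Section 3.2.1.3 assumes the lowest HbA1c may be reached as early as Week 24, speaks of a rate of rise afterwards, and gives the expectation "hence the saxagliptin therapy may be more durable".

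**Stopping.** Section 3.3.5.1 stops patients on fasting plasma glucose limits at Weeks 3, 12, 18 and 24 and on HbA1c limits from Week 30. Section 3.3.5.2 has early leavers complete the end-of-Period-C procedures; no later Week 52 measurement is described for them.

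**The concern.** LOCF is unbiased for the treatment difference only if HbA1c would have stayed level after exit, or would have moved so that the effect cancels between arms. The design gives reasons to expect neither.

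- A glipizide patient who leaves early in titration may be carried at a value above what the titrated dose would have reached. That pulls the comparison towards non-inferiority.
- A patient who leaves near the lowest point is carried without the later rise. If glipizide rises faster, as the durability hypothesis expects, this pulls the comparison against saxagliptin.

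The protocol avoids imputation for its durability test (Section 6.2, no imputation between Weeks 24 and 52) but imposes it on the non-inferiority check. The per protocol set leaves early leavers out altogether, so the full analysis set has to show whether they change the answer. If it is biased, its agreement with the per protocol result reassures less than it seems to.

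**Working it through.** **1. The plan's own figure.** Section 6.5 gives 838 randomized (419 per arm), 35% excluded from per protocol, SD 1.1, limit 0.35, true difference 0 and 95% power. 838 × 0.65 = 544.7, matching the 544 in the synopsis, or 272 per arm. SE = 1.1 × √(2/272) = 0.0943. Power = Φ(0.35/0.0943 − 1.96) = 96.0%. The stated figure is reproduced.

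**2. Precision of the full analysis set.** SE = 1.1 × √(2/419) = 0.0760. The 95% half-width is 0.149, leaving 0.35 − 0.149 = 0.201 of room at a true difference of zero.

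**3. LOCF bias.** Let f be the share of an arm missing Week 52, and D the mean of (last value − unobserved Week 52 value) among them. The bias in the saxagliptin minus glipizide difference is

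B = f_sax × D_sax − f_glip × D_glip.

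P(non-inferiority declared) = Φ((0.35 − true difference − B)/SE − 1.96).

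Two examples with 20% missing per arm and D_sax = 0:
- Glipizide leavers carried 0.3 above their eventual value: B = −0.2 × 0.3 = −0.06, towards non-inferiority.
- Glipizide leavers carried 0.3 below it: B = +0.06, against.

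**4. Sensitivity range.** The protocol gives neither f nor D. Assumed: 10–35% missing and a net between-arm drift of 0.1–0.5 among the missing.

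| Size of B | Example (share × drift) | Towards: false non-inferiority, true difference 0.35 | Against: non-inferiority shown, true difference 0 | Against: non-inferiority shown, true difference 0.15 |
|---|---|---|---|---|
| 0 | none | 2.5% | 99.6% | 75% |
| 0.01 | 10% × 0.1 | 3.4% | 99.4% | 71% |
| 0.02 | 20% × 0.1 | 4.5% | 99.1% | 66% |
| 0.03 | 10% × 0.3 | 5.9% | 98.8% | 61% |
| 0.06 | 20% × 0.3 | 12.1% | 96.8% | 45% |
| 0.08 | 20% × 0.4 | 18% | 94% | 35% |
| 0.175 | 35% × 0.5 | 63% | 63% | 5% |

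The last row is extreme: it treats the whole 35% per protocol exclusion as missing Week 52 data. Using up the 0.201 of room on average at a true difference of zero would need a net drift of 0.201/0.35 = 0.57 with 35% missing, or 1.01 with 20%.

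**5. Simulation.** Two sets of simulated trials were run with 419 per arm and assumed onset and dropout. The first used an SD of about 1.0, HbA1c stops at Weeks 30 and 39, and 2% other dropout per visit. At a true difference of 0.35:

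| Scenario | LOCF estimate, first set | LOCF estimate, second set |
|---|---|---|
| Equal onset and slopes | 0.33 | not reported |
| Slower glipizide onset plus extra early withdrawals | 0.27–0.29 | 0.31–0.33 |
| Faster glipizide rise after Week 24 | 0.38–0.39 | 0.39 |

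The second set's early-withdrawal scenarios gave false non-inferiority of about 4–11%. In the first set, the faster rise gave a bias of about 0.04–0.055 at a true difference of zero. Likelihood-based repeated measures gave 0.345–0.378 in the first set and 0.35–0.36 in the second, with a standard deviation about 15–27% larger than LOCF in the second.

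**The case against.** **Role.** The per protocol set is primary, so LOCF alone does not decide non-inferiority. This stands. The error rates above are for the full analysis set alone; how often both sets would wrongly agree has not been worked out. A reader might infer that the trial's non-inferiority conclusion is unsound, and the protocol does not support that.

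**Titration.** Three-week steps allow 20 mg by Week 9, so 18 weeks is an outer window. The Week 12 and Week 18 glucose criteria apply only to patients already on their maximum tolerated dose, and patients stopped for hypoglycaemia need not have a high HbA1c. Early saxagliptin leavers may also be carried before full response, which partly cancels. A reader might infer that LOCF always flatters saxagliptin; that does not follow. It is one possible direction.

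**Size.** One might read the bias as about a quarter of the limit in both directions, leaving the set uninterpretable. The figures do not show this: 0.08/0.35 is 23% towards non-inferiority, but 0.055/0.35 is 16% against. A false non-inferiority rate of about 30% also appeared in the first simulation set, but only with 15% against 5% extra withdrawal in titration and an SE near 0.06. Some of its scenarios had up to 52% non-completion, whereas the planned 35% covers per protocol exclusion for any reason.

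**Durability.** Saxagliptin's better durability is an expectation; the formal null is equal slopes. This stands.

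**Left to the SAP.** An SAP is promised, and model details commonly belong there. But the protocol itself fixes LOCF and makes the alternative optional, so this is a stated choice and not a missing detail.

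**The replacement.** Repeated measures is imperfect: it reached 0.378 in one scenario, and it assumes data missing at random. It was still closer to the truth than LOCF overall.

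**Conclusion.** The point holds in limited form and is worth changing. LOCF is a weak fixed choice for the one non-inferiority analysis that includes early leavers, because its flat-course assumption does not fit the protocol's titration scheme, assumed Week 24 low point, durability hypothesis and outcome-driven stopping.

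Under plausible assumptions the bias is about 0.01–0.08 points towards non-inferiority or about 0.03–0.06 against it. If the true difference is near 0.35%, false non-inferiority on this set is roughly 4–18% for biases of 0.02–0.08 (3.4% at 0.01), and higher only under more extreme assumptions. At a true difference of zero, a bias of 0.03–0.06 against saxagliptin still leaves 97–99% probability of showing non-inferiority. In between the effect is visible: at 0.15, that probability falls from 75% to 61–45%.

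The sizes rest on assumed dropout shares and drifts, and on the unadjusted SD of 1.1. Baseline adjustment would shrink the SE by an amount the protocol does not state, which would raise the false non-inferiority rate for a given bias: with an SE of 0.06, biases of 0.06 and 0.08 give about 17% and 26%.

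**What to change.** In Sections 6.3.4 and 6.4.1, make a likelihood-based repeated measures analysis the stated full-analysis-set analysis of HbA1c:

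- all observed post-baseline HbA1c to Week 52, with no imputation of post-baseline values;
- treatment, visit, treatment-by-visit, baseline and baseline-by-visit, with unstructured covariance;
- the Week 52 treatment difference and its two-sided 95% interval read against the same 0.35% limit;
- LOCF kept only as a sensitivity analysis.

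The covariance and model details can sit in the SAP; the protocol needs to make the analysis firm. A sensitivity analysis for data missing not at random, such as delta-adjusted imputation, would be a reasonable addition.

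**Cost.** Wording only. HbA1c is already measured at ten post-baseline visits from Week 3 to Week 52, and no visit, sample size or clinical rule changes. The price is a confidence interval roughly 10–25% wider than under LOCF, and reliance on a missing-at-random assumption. That assumption is credible where recorded HbA1c triggers the stop and less certain for other exits.

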6.3.5 Safety analysis set

The safety analysis set is a subset of randomized analysis set including patients who take at least one IP dose and have any safety records that can be found in the study database. Actual

treatment will be re-assigned to any patient who has taken IP dose other than what they were randomized to for the duration of the entire 52 weeks. Analysis will only use values that are actually measured.

6.4 Method of statistical analysis

6.4.1 Analysis of double-blind treatment Period C

The primary efficacy analysis to establish non-inferiority with 0.35% non-inferiority limit on the change in HbA1c from baseline to Week 52 will be performed on a per protocol analysis set using ANCOVA. The model will use treatment group as a fixed effect and baseline value as a covariate. Within the framework of the ANCOVA model, point estimates and the two-sided 95% confidence intervals for the mean change within each treatment group as well as for the differences in mean change between the saxagliptin plus metformin treatment arm and the glipizide plus metformin treatment arm will be performed. Saxagliptin plus metformin will be considered not inferior to glipizide plus metformin if the upper limit of the two-sided 95% confidence interval of the difference in change in HbA1c from baseline to Week 52 between saxagliptin plus metformin and glipizide plus metformin is less than 0.35%.

Analyses of the secondary efficacy endpoints will be performed using ANCOVA methods for change from baseline in glucose related endpoints, β -cell functions, and insulin sensitivity. The ANCOVA model will use treatment group as a fixed effect and baseline value as a covariate. Within the framework of the ANCOVA model, point estimates and the two-sided 95% confidence intervals for the mean change within each treatment group as well as for the differences in mean change between the two treatment groups will be reported.

Repeated measures analysis may be performed on selected efficacy variables over time as sensitivity analysis.

Hypoglycaemic events and body weight changes are considered as safety variables and are specified as important secondary variables supporting the treatment of saxagliptin. Proportion of patients reporting at least one episode of hypoglycaemic event over the 52-week treatment period will be compared between the two treatment groups using a two-sided Fisher's exact test. ANCOVA method comparing the two treatment groups will be used for change from baseline in body weight at Week 52, where the model will include treatment as a fixed effect and baseline as a covariate.

Durability of HbA1c will be assessed for each of the two treatment groups from mean slopes of the regressions of change from Week 24 in HbA1c on treatment duration from Week 24 to Week 52. All patients with a pair of HbA1c levels at Week 24 and post Week 24 will be included. Weeks on randomized treatment period will be used as a regressor. Only observed values between the two visits, inclusive, will be used for the analysis.

Three secondary variables (proportion of patients reporting hypoglycaemic events and change from baseline in body weight, and mean slopes of the regressions of change from baseline in HbA1) have been identified for special consideration in this study, in addition to the primary efficacy variable (NI HbA1c). In order to control overall type 1 error rate of the study, a fixed-

sequence test will be adopted with respect to the 4 hypotheses, ie, the testing will be sequentially performed in the following order:

- 1. Non-inferiority comparison of HbA1c, if NI is demonstrated then statistical inference proceed step 2, otherwise inference will stop.
- 2. Superiority tests for hypoglycaemic event if significant (p<0.05) in favour of saxagliptin and metformin treatment group then statistical inference proceed step 3, otherwise inference will stop.
- 3. Superiority test for weight changes, if significant (p<0.05) in favour of saxagliptin and metformin treatment group then statistical inference proceed step (4), otherwise inference will stop.
- 4. Superiority inference for durability.

All comparison will be two-sided at the 5% significance level.

All other secondary efficacy variables are supplemental and not included in the multiple comparison scheme as outlined above.

Summary tables will be presented for proportions of patients achieving glycaemic therapeutic response.

Change from baseline in AUC from 0 to 180 minutes for glucose, insulin, C-peptide and glucagon will be analyzed by ANCOVA method similar for the primary endpoint. The lipid endpoints will be log-transformed before ANCOVA analysis. In which case log baseline will be used as a covariate and treatment as a fixed effect in the model. Within the framework of the ANCOVA model, point estimates and the two-sided 95% confidence intervals will be first constructed in the logarithmic scale. By taking the anti-logarithms, estimates and confidence intervals for the true geometric means and ratios of true geometric means will be displayed.

In general, analyses of all secondary efficacy endpoints, other than durability as specified variable of special interest, will be carried out by means of linear models using baseline value as a covariate as for the primary variable. Results will be reported as point estimates, 95% confidence intervals.

Subgroup analyses will be described in the SAP.

Analysis for safety and tolerability endpoints, other than proportion of patients with at least one hypoglyceamic event and weight changes, will be summarized by descriptive statistics or frequency tables and/or graphic method. There are no hypotheses proposed a priori for these safety endpoints.

6.4.2 Pharmacokinetic measurements and variables

The plasma concentrations obtained by sampling of individual patients will be used to build a pharmacokinetic model to estimate pharmacokinetic parameters (eg, apparent oral clearance (CL/F), apparent oral volume of distribution (Vd/F), and absorption rate constant (ka)). Possible covariate effects on pharmacokinetic parameters (eg, gender effect on CL/F) may be identified and quantified. Using model-based simulations, the pharmacokinetic parameters will be used to compute individual exposure measures (eg, AUC, minimum observed concentration (Cmin)). Relationships between these exposure measures and various efficacy and safety endpoints may be explored. The pharmacokinetic data derived from this study may be pooled with similar data from other studies and the results described in a separate report.

